This document is confidential and is to be distributed for review only to investigators, potential investigators, consultants, study staff, and applicable independent ethics committees or institutional review boards. The contents of this document shall not be disclosed to others without written authorization from WCM.

Weill Cornell Medicine

Institution Name

M. [name], PhD

June 29, 2021

Principal Investigator's Name

Principal Investigator's Signature

Date

List of Abbreviations

AE	Adverse Event
CFR	Code of Federal Regulations
COA	Center on Aging
CRF	Case Report Form
CTSC	Clinical Translational Science Center
FDA	Food and Drug Administration
FMS	FibroMyalgia Syndrome
GCP	Good Clinical Practice
HIPAA	Health Insurance Portability and Accountability Act of 1996
ICF	Informed Consent Form
IRB	Institutional Review Board
LARKSPUR	Lessons in Affect Regulation to Keep Stress and Pain UndeR control
NYP	NewYork-Presbyterian
PA	Positive Affect
PHI	Protected Health Information
PI	Principal Investigator
REDCap	Research Electronic Data Capture
WCM	Weill Cornell Medicine

1. Protocol Summary

Full Title:	Positive Affect as a Source of Resilience for Adults in Chronic Pain
Short Title:	LARKSPUR Study
Principal Investigator:	M. [name], PhD (WCM) [name] (Cornell)
Study Description:	Our goal for this study is to evaluate the feasibility, acceptability, and effect size of a previously developed online positive affect (PA) skills intervention—LARKSPUR (Lessons in Affect Regulation to Keep Stress and Pain UndeR control)—in a sample of older adult patients with fibromyalgia syndrome (FMS).
Sample Size:	N= 150
Enrollment:	This study will enroll 150 subjects and screen up to 1,200 subjects
Study Population:	Older adults 50 years of age or older with a physician confirmed diagnosis of FMS, or a self-report physician diagnosis corroborated by a screening measure, that will be stratified by Hispanic, non-Hispanic Black, or non-Hispanic other (e.g., White, Asian).
Enrollment Period:	2 years
Study Design:	This is a longitudinal, randomized behavioral intervention feasibility study with internet trainings, daily reporting, and surveys using REDCap and BrightOutcome for data collection.
Description of Sites/ Facilities Enrolling	
Participants:	We will be enrolling participants only through WCM/NYP and will be recruiting participants through EPIC, physician referral, flyers, letters, social media, and direct recruitment.
Study Duration:	September 30, 2024
Participant Duration:	4 months
Primary Objective:	To maximize relevance and acceptability of content and delivery of LARKSPUR intervention among patients with FMS, a chronic pain population with known deficits in PA. This aim will establish the feasibility (recruitment and retention) and acceptability (helpfulness, satisfaction, and impact) of the multicomponent LARKSPUR intervention in patients with FMS.
Secondary Objectives:	To conduct a randomized pilot trial to estimate the effect size of the LARKSPUR intervention in FMS pain (primary outcome), as well PA, depressive symptoms, physical functioning, and stress appraisals (secondary outcomes), and explore racial/ethnic disparities. We hypothesize that intervention participants will report more frequent PA, decreased depressive symptoms, enhanced physical functioning, improved stress appraisals, and reduced FMS pain (intensity and interference) immediately following the intervention (approximately 8 weeks), and at 1-month post-intervention.
Exploratory Objectives:	Not Applicable
Secondary Endpoints:	Not Applicable

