- Week 4: Positive Reappraisal and Gratitude
- Week 5: Acts of Kindness
- Week 6: Wrap-Up

The following table is the LARKSPUR intervention content.

Table 1. Intervention Content

Week 1	Noticing and Savoring Positive Events	Recognizing cognitive biases that can lead to discounting or failing to remember positive events. Skills for scheduling pleasant events according to level of pain
	Exercises	Daily positive events journal
Week 2	Strengths and Activation	Support for acknowledging strengths even in the presence of pain-related limitations. Emphasis on setting small, attainable goals and working up to challenging goals gradually. How to select goals that will provide pleasure or mastery experiences.
	Exercises	Daily strengths journal (record ways a personal strength or talent was used) Activity journal
Week 3	Mindfulness	Using present-focused awareness to combat rumination about chronicity of pain and pain-related limitations Using acceptance to tolerate unpleasant situations with less negative emotion
	Exercises	Select an everyday activity to do mindfully Mindful breathing recorded meditation (10 minutes)
Week 4	Positive Reappraisal and Gratitude	Role of negative cognitions in causing or maintaining stress and contributing to pain
	Exercises	Daily reappraisal journal Daily gratitude journal
Week 5	Acts of Kindness	Include benefits of compassion toward self and others (e.g., decreased stress and pain; improved relationships) Small prosocial acts that can be performed even if one is relatively socially isolated or has limited mobility
	Exercises	Do something nice for someone else each day and record it in a daily kindness journal
Week 6	Wrap-Up	Review the LARKSPUR course, reflect on skills learned, and make a plan for continued practice.

Randomization. Once participants complete consent and baseline questionnaire, participants will be randomized 1:1 to LARKSPUR (n = 75) or an emotion reporting only attention control condition (n = 75) stratified by race/ethnicity. The random number sequence will be generated and uploaded into REDCap by a non-data collecting co-investigator under the guidance of the study statistician and REDCap/CTSC personnel. All participants will know their intervention/attention control status.

LARKSPUR intervention (n = 75). The LARKSPUR intervention will be based on our current online positive affect intervention which consists of skills for increasing the frequency of positive emotions, beginning

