4.4 Strategies for Recruitment and Retention

We will recruit fibromyalgia patients from offices at Weill Cornell Medicine/NewYork-Presbyterian (e.g., the Center on Aging (COA), the Cornell Internal Medicine Associates (CIMA), and the Iris Cantor Health Center). Co-PI [name], PI of the Cornell Roybal Center, has established a successful track record recruiting chronic pain patients for Roybal-supported research studies at Weill Cornell Medicine/NewYork-Presbyterian.

A total of 150 fibromyalgia patients will be recruited across Aims 1-2 once they have been identified by research and referring physicians confirmed to meet eligibility criteria. Based on prior recruitment at WCM/NYP we anticipate recruiting double the number of females than males, and will target enrollment to an equal number of non-Hispanic Black, Hispanic, or non-Hispanic other (e.g., White, Asian) equally between males and females. Participants will open-endedly self-report their race and ethnicity; the research team will ensure that the randomization process is stratified by Hispanic, non-Hispanic Black, and non-Hispanic other (e.g., White, Asian).

Normal patient participants will be recruited via physician-referred agree to contact sheets (paper or REDCap survey), flyers, and/or in-person recruitment. Physicians will utilize an Agree to Contact sheet that potential participants fill out with their contact information (phone, email, and/or mailing address) and sign agreeing to be contacted directly for the study by any of these methods.

Flyers will be distributed throughout WCM/NYP locations (including the Center on Aging), and distributed at senior centers, community centers, and community events. Additionally, co-investigators may approach potential participants in WCM/NYP offices (e.g. the Center on Aging), and ask if they would be interested in the study, when it is safe to do so under COVID-19 considerations. Trained co-investigators may either screen the participants at recruitment sites and/or ask for their contact information via the Agree to Contact sheet to be followed up at a time convenient for the potential participant.

Research staff will ask physicians at WCM/NYP, to review their patient lists and identify potential participants based on eligibility criteria both directly (e.g. email) and at department meetings. Research staff may also request EPIC provider reports based on eligibility requirements to reach out

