to WCM/NYP physicians for permission to contact potential patient participants. Research staff will set EPIC search criteria to draw names from all networked EPIC databases accessible to Weill Cornell Medicine staff. Identified potential participants will be contacted via recruitment letter, email, or Weill/EPIC Connect. Recruitment letters may also be sent to potential participants via EPIC pool of WCM/NYP Consent to be Contacted for Research (CCR) patients and chart review to determine potential eligibility. Potential subjects will be sent a letter informing them of the study and that they will be contacted by a co-investigator who will assess interest in participating in the study. The letter will also provide a contact phone or email address that these patients can reach out to express their interest/disinterest for participation in the study.

Additional efforts will rely on making study information available on online platforms. Online platforms may include, but are not limited to: FMS interest pages on Facebook, participant registries, online bulletin boards, mobile apps and websites, etc. Methods include, but are not limited to: posting flyers, posting messages describing the project and inviting interested participants to contact study members (see "Social Media Posting" document), including study information in e-newsletters, etc. Permission from group administrators will be received prior to posting on any social media group platform. In addition, online research match databases including but not limited to ResearchMatch.org and the Institute for Translational Health Sciences will be added as a recruitment method.

Eligible participants will be compensated up to \$142 for completing the study. Participants will receive \$25 for each of the three study assessments (baseline, post-intervention, and 1-month follow up), up to \$42 (\$2 per survey) for the daily 5-10-minute surveys following the study assessments, and \$25 for the feedback survey. Activities completed during the 6-8 weeks of interaction on BrightOutcome will not be compensated.

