### 6.4.1 Primary Outcomes

#### 6.4.1.1 Recruitment as Measured by Rates of Enrollment

Enrollment is assessed based on the percentage of participants recruited into the study out of all total eligible participants.

*% Enrollment* = (number of recruited participants meeting eligibility requirements and enrolled into the study) / (number of recruited participants) \* 100.

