**7      Sample Size**

Given that the primary purpose of this study is to assess the feasibility of methods and procedures to be used in a larger, fully powered trial of LARKSPUR, sample size was chosen based on feasibility indicators (recruitment, retention, adherence) rather than on formal power calculations, as appropriate for the pilot nature of the study [see 1]. For quantitative pilot studies, sample sizes of 30 per treatment arm have been proposed to establish feasibility [2]. To allow for attrition between end-of-trial and follow-up, we aimed to recruit 45 per group (intervention and control). Findings from subgroup analyses should therefore be interpreted with caution and call for further confirmatory randomized trials [3].

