### 10.1 Primary Efficacy Analysis

The Recruitment Primary Outcome will be calculated as described in Section 6.4.

The Retention Primary Outcome treatment group percentages will be compared using Boschloo's Test at the 2-sided 5% significance level under the null hypothesis that retention rates are equal between treatment groups [15]. The maximum likelihood estimate of the odds ratio of treatment retention to control retention will be computed with a 2-sided 95% confidence interval and p-value.

The Rating of Recommending Intervention to Friend and Rating of Recommending Intervention to Those with Chronic Pain items will be summarized using an ordinal regression (proportional odds) model without predictors (i.e., the ordinal properties of the Likert scales of these two items will be respected by estimating the average rating adjusted for the cumulative category response probability distribution) [16]. The modified Intention-to-Treat sample described in Section 8.1 will be used.

The Length of Intervention Time will be calculated as described in Section 6.4.

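### The recruitment endpoint has no time element, two different denominators and two different targets, so it cannot show whether accrual went to plan

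*Protocol*

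**What the plan says.** - **Plan in the protocol.** Section 1, Enrollment: "This study will enroll 150 subjects and screen up to 1,200 subjects". The same table gives an enrolment period of 2 years. Section 3, Randomization, splits the total: "participants will be randomized 1:1 to LARKSPUR (n = 75) or an emotion reporting only attention control condition (n = 75").
- **Plan in the SAP.** Section 7 gives a different number: "we aimed to recruit 45 per group (intervention and control").
- **Endpoint, in words.** SAP 6.4.1.1: "Enrollment is assessed based on the percentage of participants recruited into the study out of all total eligible participants".
- **Endpoint, as a formula.** The same section then writes it, times 100, as "number of recruited participants meeting eligibility requirements and enrolled into the study) / (number of recruited participants".
- **Analysis.** SAP 10.1 says only: "The Recruitment Primary Outcome will be calculated as described in Section 6.4". SAP 6.1 limits statistical testing among the primary outcomes to retention.
- **Composition.** Protocol 4.4 says the study "will target enrollment to an equal number of non-Hispanic Black, Hispanic, or non-Hispanic other", and randomisation is stratified by these three groups.

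**The concern.** Aim 1 is to establish feasibility, with recruitment named as one of its two components, and SAP section 7 says the study's main purpose is to prepare a larger trial. Planning that trial requires knowing how many people can be randomised per unit of time. A percentage of eligible or recruited people answers a different question, namely how many of those reached go on to join. It takes the same value whether the sample is filled on schedule or long after it.

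Two further gaps make the result hard to use. In the sentence the word recruited describes the numerator; in the formula it describes the denominator. The first version measures uptake among eligible people. The second mixes eligibility with uptake. Also, with 150 in one document and 90 in the other, the reader cannot tell which number recruitment should be judged against.

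**Working it through.** **Inputs.** 150 enrolled, up to 1,200 screened, 2 years = 24 months (Protocol section 1); 75 + 75 (Protocol section 3); 45 per group (SAP section 7); three strata targeted equally (Protocol 4.4). The documents state no monthly rate and no expected percentage, so there is no planned figure for the endpoint to reproduce.

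**Step 1, the target.** 75 + 75 = 150 agrees with the protocol summary. 45 + 45 = 90 does not; it is 90/150 = 60% of it.

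**Step 2, implied rates over 24 months.**
- Target 150: 150/24 = 6.25 per month, or 6.25/3 = 2.08 per stratum.
- Target 90: 90/24 = 3.75 per month, or 3.75/3 = 1.25 per stratum.

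**Step 3, what the percentage shows.** Neither denominator is given a planned size, so the number screened stands in for it here (an assumption). Totals of 720 and 600 screened, and the 40 months, are illustrative.

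| Randomised | Denominator | Months | Percentage | Per month |
|---|---|---|---|---|
| 150 | 1,200 | 24 | 12.5% | 6.25 |
| 150 | 1,200 | 40 | 12.5% | 3.75 |
| 90 | 720 | 24 | 12.5% | 3.75 |
| 75 | 600 | 24 | 12.5% | 3.12 |
| 90 | 1,200 | 24 | 7.5% | 3.75 |

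Rows 1 and 2 show that a delay is always invisible. Rows 3 and 4 show that a shortfall is invisible when the denominator falls in proportion. Row 5 shows that it is visible when the full 1,200 are screened.

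**Step 4, the denominator.** With 150 randomised, the percentage is 12.5% of 1,200, but 25%, 50% or 75% if 600, 300 or 200 people (assumed) are the ones counted.

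**Step 5, would a rate be informative?**
- 150 in 24 months: 6.25 ± 1.96 × √150/24 = 6.25 ± 1.00, about 5.2 to 7.3 per month.
- 90 in 24 months: exact Poisson 95% interval 3.0 to 4.6 per month, which excludes 6.25.
- One stratum of 50: 2.08 ± 1.96 × √50/24, about 1.5 to 2.7. One stratum of 30: 1.25 ± 1.96 × √30/24, about 0.8 to 1.7. These overlap, so stratum rates are only descriptive.

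**The case against.** **Accrual is covered elsewhere.** Protocol 4.4 has accrual reviewed at weekly meetings. SAP 4.2 and 9 promise means, medians and standard deviations of enrolment rates, and SAP 9.1 plans a disposition summary and flow diagram. The number enrolled will therefore be reported. This stands in part: a reader could set that number against the two years. But the weekly review is operational, no unit is given over which a mean enrolment rate would be taken, and the disposition summary is not described as containing time. None of this makes accrual an outcome.

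**Race and ethnicity are covered.** SAP 10.2 plans exploratory summaries of primary outcomes by ethnicity and race. This also stands in part, but those summaries would apply the same percentage without time.

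**Stronger readings that the documents do not support.**
- A reader might infer that the endpoint always gives the same value whether or not the plan is met. That is true of time but not of number, as 90/1,200 = 7.5% shows.
- A reader might take 90 randomised as failure. It is exactly the SAP's own target.
- A reader might take 12.5% as the planned yield. The 1,200 is an upper limit on screening, so 12.5% is only the lowest yield that still reaches 150.
- A reader might infer that mixing clinic sources with online ones such as "FMS interest pages on Facebook, participant registries, online bulletin boards, mobile apps and websites" distorts the percentage. That requires yields to differ by source, and the documents give none. With assumed clinic and online yields of 20% and 5%, the pooled figure moves from 8% to 17% as the clinic share goes from 20% to 80%. With 15% and 10% it moves from 11% to 14%, and with equal yields it does not move. Neither document shows that recruitment source is recorded.

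**Conclusion.** The concern holds in a limited form. The recruitment endpoint contains no calendar time, so it cannot show whether the intended number was reached in the enrolment period. It can also conceal a shortfall, though it need not. The percentage itself is ambiguous because sentence and formula use different bases. The benchmark is unsettled between 6.25 and 3.75 per month, assuming both targets run over the protocol's 24 months. The SAP is dated later than the protocol and may reflect a revised target, but neither document says so.

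This does not affect participants or the comparisons between groups. It does weaken the answer to the study's main feasibility question, and it is worth correcting before the results are reported.

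**What to change.** 1. Reconcile the recruitment target between Protocol sections 1 and 3 and SAP section 7. If it was changed, state when and why.
2. In SAP 6.4.1.1, define one denominator for the enrolment percentage, say who is counted in it, and make sentence and formula agree.
3. Add to SAP 6.4.1.1 and 10.1 the number randomised per month, counted from the opening to the close of enrolment, with a Poisson 95% confidence interval. Set it against the reconciled target: 6.25 per month if 150, 3.75 if 90, over 24 months. Give the same rate descriptively for each of the three randomisation strata.
4. Show the percentage by recruitment source only if source was recorded. Do not use 12.5% as a benchmark.

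The cost is a short SAP edit and one small table. Item 3 needs only randomisation dates and strata, which should be recoverable because the randomisation sequence is held in REDCap. It adds no test, so it is consistent with SAP 6.1. The downside is one more descriptive result, which may look less favourable than the percentage alone.

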1.1 Study Objectives

Our goal for this study is to evaluate the feasibility, acceptability, and effect size of a previously developed online positive affect (PA) skills intervention—LARKSPUR (Lessons in Affect Regulation to Keep Stress and Pain UndeR control)—in a sample of patients with fibromyalgia syndrome (FMS).

1.1.1 Objectives

- 1) To maximize relevance and acceptability of content and delivery of LARKSPUR intervention among patients with FMS, a chronic pain population with known deficits in PA. This aim will establish the feasibility (recruitment and retention) and acceptability (helpfulness, satisfaction, and impact) of the multicomponent LARKSPUR intervention in patients with FMS.
- 2) To conduct a randomized pilot trial to estimate the effect size of the LARKSPUR intervention in FMS pain (primary outcome), as well PA, depressive symptoms, physical functioning, and stress appraisals (secondary outcomes) and explore racial/ethnic disparities. We hypothesize that intervention participants will report more frequent PA, decreased depressive symptoms, enhanced physical functioning, improved stress appraisals, and reduced FMS pain (intensity and interference) immediately following the intervention (approximately 8 weeks), and at 1-month post-intervention.

1.1.2 Hypotheses / Research Questions

We hypothesize that the intervention will lead to more frequent daily PA, which, in addition to directly affecting depressive symptoms, will also have indirect effects through enhanced physical functioning and improved stress appraisals (*resilience mechanisms*). Decreased depressive symptoms, enhanced physical functioning, and improved stress appraisals, in turn, are hypothesized to lead to reduced FMS pain (*resilience outcomes*).

2. Background and Significance

Chronic non-cancer pain affects as many as 100 million Americans and is associated with significant functional limitations and physical disability. Standard behavioral therapies typically focus on minimizing negative thoughts and emotions associated with pain and yield only modest treatment effects. Efforts are therefore needed to develop more effective psychological treatments for chronic pain by identifying new targets for intervention. We propose to pilot test a resilience-based intervention that targets positive affect (PA) in fibromyalgia syndrome (FMS) patients, a chronic pain population with known deficits in PA and an inability to regulate PA in the face of pain. Our goal is to conduct a randomized pilot trial of LARKSPUR (Lessons in Affect Regulation to Keep Stress and Pain UndeR control), an online-delivered PA skills intervention. Our central hypothesis is that our LARKSPUR program will (a) show acceptability and feasibility in engaging and retaining FMS patients and (b) demonstrate greater improvements in PA and FMS-related pain and functional impairment.

This proposal for pilot data collection will lay the foundation for a high-quality randomized trial for people with FMS. The proposed work holds promise as an effective, low cost, scalable, and readily implementable novel non-pharmacologic intervention to help people cope with FMS. By demonstrating the feasibility, acceptability, and preliminary efficacy of the LARKSPUR intervention, we hope to improve quality of life, as well as the options available for care for millions of people who suffer from FMS.

3. Study Design and Methods

The LARKSPUR online intervention will be hosted and maintained by a HIPAA compliant application developer (BrightOutcome) via a web-based platform. The order of the skills has been finalized and skills are unlocked by week as follows:

- Week 1: Noticing and Savoring Positive Events
- Week 2: Strengths and Activation
- Week 3: Mindfulness
- Week 4: Positive Reappraisal and Gratitude
- Week 5: Acts of Kindness
- Week 6: Wrap-Up

The following table is the LARKSPUR intervention content.

Table 1. Intervention Content

Week 1	Noticing and Savoring Positive Events	Recognizing cognitive biases that can lead to discounting or failing to remember positive events. Skills for scheduling pleasant events according to level of pain
	Exercises	Daily positive events journal
Week 2	Strengths and Activation	Support for acknowledging strengths even in the presence of pain-related limitations. Emphasis on setting small, attainable goals and working up to challenging goals gradually. How to select goals that will provide pleasure or mastery experiences.
	Exercises	Daily strengths journal (record ways a personal strength or talent was used) Activity journal
Week 3	Mindfulness	Using present-focused awareness to combat rumination about chronicity of pain and pain-related limitations Using acceptance to tolerate unpleasant situations with less negative emotion
	Exercises	Select an everyday activity to do mindfully Mindful breathing recorded meditation (10 minutes)
Week 4	Positive Reappraisal and Gratitude	Role of negative cognitions in causing or maintaining stress and contributing to pain
	Exercises	Daily reappraisal journal Daily gratitude journal
Week 5	Acts of Kindness	Include benefits of compassion toward self and others (e.g., decreased stress and pain; improved relationships) Small prosocial acts that can be performed even if one is relatively socially isolated or has limited mobility
	Exercises	Do something nice for someone else each day and record it in a daily kindness journal
Week 6	Wrap-Up	Review the LARKSPUR course, reflect on skills learned, and make a plan for continued practice.

Randomization. Once participants complete consent and baseline questionnaire, participants will be randomized 1:1 to LARKSPUR (n = 75) or an emotion reporting only attention control condition (n = 75) stratified by race/ethnicity. The random number sequence will be generated and uploaded into REDCap by a non-data collecting co-investigator under the guidance of the study statistician and REDCap/CTSC personnel. All participants will know their intervention/attention control status.

LARKSPUR intervention (n = 75). The LARKSPUR intervention will be based on our current online positive affect intervention which consists of skills for increasing the frequency of positive emotions, beginning

with basic skills for recognizing and savoring positive events and progressing to more complex skills such as goal-setting and acts of kindness.

A week will consist of 1-2 days of didactic material and 5-6 days of real-life skills practice and reporting. Participants cannot skip ahead and can only progress to the next lesson if they have completed the current one, but they can return to old lessons or exercises if they choose. As part of the daily home practice, intervention participants will be asked to complete the daily emotion check-in that comprises the attention control condition (which takes about 5 minutes to complete). Based on past studies, we estimate the time to read through a skill to be about 15 minutes per skill. We also encourage daily interaction with the website (home practice, reporting emotions) and estimate the time involved to be an additional about 10 minutes. Both the LARKSPUR intervention and emotion-reporting attention control conditions, including all home practice and assessments, will be done over the internet from the participant's home, or any other location of their choice. The intervention content, emotion check-in, and are all mobile-enabled so can be completed on desktop, laptop, tablet, or smartphone with web browser access.

Attention Control Condition (n = 75). We sought an attention control condition that provided something to engage participants, but was not expensive or burdensome. In past research we have established that emotion reporting is acceptable as an attention control condition (retention rates of ~80%, similar to or higher than for the intervention), and that participants perceive it as being beneficial, providing some of the features of a placebo control. In this daily emotion-reporting attention control condition, participants will be asked to report how they are feeling daily for 6-8 weeks which will be emailed to control participants.

Participants in the attention control condition will be prompted to report on positive and negative emotions experienced in the past day and pain level in the past day, going back a maximum of 24 hours. Based on past studies, we expect that this reporting will require approximately 5 minutes per day. Note that participants in the LARKSPUR intervention condition will also be completing the daily reporting of emotions as part of their home practice. The control group will be completing the same number of assessments as the intervention condition at the same time points (baseline, post-intervention, 1-month follow-up).

[figure not shown]
Data collection, transfer, security, and management. Data for the study will come from self-report through online. Self-report data will be collected via online assessment (REDCap) at baseline, during the 6-8-week intervention/control (BrightOutcome), immediate post intervention/control, and at 1-month follow-up. In addition, one week of daily stress and emotion surveys coinciding with each of the three assessments, for a total of 21 days outside the intervention/control period, will be collected via REDCap. The baseline, post-intervention/control, and 1-month follow-up surveys will last 60 and no more than 75 minutes, and may also be done by phone or videoconference in cases of preference, or due to retention follow-up. With participant permission, phone and/or videoconference calls may be recorded for the purpose of accurate data collection. The recordings will be deleted after the study is completed and participation is **not** contingent on the participant's agreement to be recorded. Participants will choose whether or not to authorize recordings when completing their informed consent process.

Data from the online intervention platform will be securely stored on Weill Cornell Medicine and BrightOutcome servers, accessible only to IRB-approved co-investigators and BrightOutcome staff. These data include number of log-ins, completed home exercises, number of skills completed, and data from the daily emotion reporting surveys. All data used for analysis will be de-identified, and no identifiable data will ever be stored locally on staff computers and no data are stored locally on participants' devices.

Measures. All participants will complete self-report questionnaire measures at baseline, post-intervention, and 1-month follow-up on-line via REDCap or by phone. Participants will complete one week of daily 5-10-minute surveys upon completion of each the three assessments, for a total of 21 days. They will also complete 5-minute daily check-in surveys during the intervention/control period of 6-8 weeks as outlined below in schedule of assessments.

Our selection of measures is guided by the theoretical model in Figure 1.

Figure 1. Theoretical Model

Specifically, we hypothesize that the intervention will lead to more frequent daily PA, which, in addition to directly affecting depressive symptoms, will also have indirect effects through enhanced physical functioning and improved stress appraisals (*resilience mechanisms*). Decreased depressive symptoms, enhanced physical functioning, and improved stress appraisals, in turn, are hypothesized to lead to reduced FMS pain (*resilience outcomes*). The proposed pilot will lay the foundation for a future high-quality, adequately powered trial that will explore theoretical moderators, thereby identifying individuals most likely to benefit from the LARKSPUR intervention (*resilience resources*). Finally, it is anticipated that the proposed project will foster cross-campus collaborations (i.e., Weill Medical College, Cornell University) that will advance research on rheumatic and autoimmune diseases (including FMS), and culminate in the development of a novel non-pharmacologic therapeutic approach that is effective, low cost, and easily disseminated.

4. Study Design

